6.2 Randomisation

N/A.

6.3 Interim Analysis

N/A

7. Statistical Analysis

7.1 General

CONFIDENTIAL AND PROPRIETARY

This document contains information that is confidential and proprietary to Smith & Nephew PLC and Smith & Nephew, Inc. and is intended for use only by Smith & Nephew and its manufacturer. It shall not be reproduced or copied in whole or in part, nor shall the contents be disclosed by any means without prior written permission from Smith & Nephew, nor shall anyone make any use of it that is contrary to the expressed or implied wishes of Smith & Nephew.

Statistical Analysis Plan	 smith&nephew
A Retrospective Study of the NAVIO Robotic-assisted Surgical System	Number: 16-NPFS-11
	Version: Final 1.0, Jan 29, 2018
	Page: 13 of 25

Smith & Nephew's Global Biostatistics group would carry out the statistical analysis for this study. Unless otherwise stated, all statistical significance tests and the hypothesis test would be two-sided, performed at the 5% significance level (i.e. $\alpha = 0.05$). Where appropriate, the resulting p-values would be quoted and if applicable, the corresponding 95% two-sided confidence intervals (CIs) would be generated. All p-values would be rounded to three decimal places; p-values less than 0.001 would be presented as ' <0.001 ' in all tables.

For data summaries, categorical and ordinal variables would be summarized using frequency and percent. Continuous variables would be summarized using characteristics such as number of observations, mean, median, standard deviation, minimum and maximum values. All analyses would be performed in SAS version 9.3 or a more recent version.

All demographic and baseline variables as well as effectiveness endpoints would be summarized using both the safety and per protocol populations unless otherwise specified. For the primary endpoint, the safety population would be used as the primary analysis population while the per protocol population would be used for sensitivity analysis of the analysis of the primary endpoint. The secondary endpoints would be summarized using only the safety population. All safety endpoints would be summarized using the safety population.

All statistical comparisons of the data would provide the test statistic used as well as its distributional assumptions. In general, an equivalent non-parametric test would be used as alternative to the parametric where means are markedly different from medians thus increasing the likelihood that violations of normality assumptions would occur.

Subject data listings would be created to provide supporting information for pertinent tables.

CONFIDENTIAL AND PROPRIETARY

This document contains information that is confidential and proprietary to Smith & Nephew PLC and Smith & Nephew, Inc. and is intended for use only by Smith & Nephew and its manufacturer. It shall not be reproduced or copied in whole or in part, nor shall the contents be disclosed by any means without prior written permission from Smith & Nephew, nor shall anyone make any use of it that is contrary to the expressed or implied wishes of Smith & Nephew.

Statistical Analysis Plan	 smith&nephew Number: 16-NPFS-11 Version: Final 1.0, Jan 29, 2018 Page: 14 of 25
A Retrospective Study of the NAVIO Robotic-assisted Surgical System	

7.2 Analysis Populations

Safety Population

This is defined as the population of subjects who receive the investigational study device.

Per Protocol Population

The per protocol population is the subset of subjects in the safety population who are compliant with the protocol by satisfying the following criteria: (a) meeting all inclusion/exclusion criteria (b) attend follow-up assessments and do not have significant protocol deviations.

Subjects who have a device revision would retain membership in the per protocol population unless any of the above two specifications is met. The final decision on which deviations would be classified as significant would be finalized prior to database lock.

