## 3. STUDY DESIGN

This is a retrospective, multi-center, cohort study with prospective follow-up and comparison to historical control to collect 2-year safety and effectiveness data on 128 subjects, at up to 10 sites in the United States and Europe, who have undergone Navio System-assisted UKR.

Subject data will be retrospectively evaluated at the pre-operative, operative, and any available postoperative follow-up visits as well as prospectively evaluated at the 2-year (-3months) or greater postoperative follow-up visit.

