## 6. STUDY PROCEDURES

### 6.1. Study Schematic

The intervals and schedule of events are provided in Table 1.

	Retrospective Data Collection 				Prospective Data Collection 
	Screening and Enrollment	Pre-operative	Operative / Discharge	Follow-up	
Informed Consent	✓ 				
Inclusion/Exclusion	✓				
Demographics/ Medical History		✓			
Operative and Discharge Data Collection			✓		
Implant Status 				✓	✓
Knee Society Score (KSS)		✓		✓	✓
VR-12		✓		✓	✓
Radiographic Assessment		✓	✓	✓	✓
Adverse Event Assessment			✓	✓	✓
End of Study/Exit				✓*	✓

Given the retrospective-prospective study design, data will be collected to the extent it is available.

Visit may occur in an office or remotely. If completed remotely (e.g. telephone call, mailing of subject questionnaires and/or any other means), secondary endpoint data will be collected to the extent possible.

Informed consent/waiver of informed consent from the IRB/EC must be obtained prior to retrospective and prospective data collection.

Subjects who have undergone a revision procedure of the study knee will be considered terminated from the study from the date of the revision. Study related data will not be collected following the date of the revision.

\*if applicable

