#### F. Revisions

Subjects who have undergone a revision procedure of the study knee will be considered terminated from the study from the date of the revision. Study-related data will not be collected following the date of the revision. The appropriate CRFs will be completed for these subjects to document the details of study termination and revision.

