### **9.3. Evaluability**

All subjects that receive a study device are considered study participants. The following study populations and analysis sets will be defined:

- Safety Population: This will include all subjects that received the study device.
- Full Analysis Set (FAS): This will include all subjects that received the study device.
- Per Protocol Population (PP): This will include all subjects that received the study device, meet the inclusion/exclusion criteria, attend the follow-up assessments, and have no significant protocol deviations. Subjects that are required to be withdrawn from the study under the protocol (e.g. due to revision) will be included regardless of attendance of follow-up visits unless they are deemed to have significant protocol deviations or failed to meet the inclusion/exclusion criteria.

Statistical analysis will be performed using each of the patient populations as follows: analysis of the primary, secondary efficacy objectives will be performed separately using both the FAS and the PP Population. All safety analyses will utilize the Safety Population.

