Cumulative proportions of subjects with implant survivorship at 2 years would be calculated and displayed accordingly. Subjects who complete the study without a revision would be censored at their last known date in the study. A subject who prematurely discontinues from study as a result of death or for any other reason would be censored at the date this event occurred. A subject who is lost to follow-up would be censored at the last known contact date. The Kaplan-Meier estimate for implant survivorship would be presented with the corresponding two-sided 95% Confidence Intervals (CIs). This study's hypothesis test would only be carried out at the end of the study at 2+ years (96 weeks). From this test, if the lower limit (LL) of the 95% two-sided CI for $S(t = 2 \text{ years}) > (\pi_0 - \delta) = 88.7\%$, then H_0 will be rejected in favor of H_a (i.e. demonstration of non-inferiority of the investigational device) otherwise H_0 would not be rejected. Kaplan-Meier estimates for implant survivorship would also be non-inferentially estimated at the intermediate time points of 6 months (24 weeks), 1 year (48 weeks), and at 18 months (72 weeks) as well as subsequently at 30 months (120 weeks).

The primary endpoint would be analyzed using the safety population as the primary analysis population while the per protocol population would be used for sensitivity analysis.

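### SAP 7.2 words the per-protocol rule for revised subjects backwards, and correcting the slip alone still leaves out the attendance exemption in protocol 9.3

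*SAP*

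**What the plan says.** SAP 7.2 builds the per-protocol population from safety-population subjects who satisfy two criteria: "a) meeting all inclusion/exclusion criteria (b) attend follow-up assessments and do not have significant protocol deviations". It then adds a rule for subjects with the primary event: "Subjects who have a device revision would retain membership in the per protocol population unless any of the above two specifications is met".

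Protocol 9.3 covers the same subjects. Those whom the protocol requires to be withdrawn, with revision given as the example, "will be included regardless of attendance of follow-up visits unless they are deemed to have significant protocol deviations" or failed the eligibility criteria.

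Three other places bear on how the rule works:

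- **Follow-up schedule.** Protocol 3 has subjects evaluated at "any available postoperative follow-up visits as well as prospectively evaluated at the 2-year (-3months) or greater postoperative follow-up visit". Only the 2-year visit has a set time.
- **End of participation.** Protocol 6.1, footnote 4: "Subjects who have undergone a revision procedure of the study knee will be considered terminated from the study from the date of the revision". Protocol 7.1 F: "Study-related data will not be collected following the date of the revision".
- **Use of the population.** SAP 7.1 states that "the per protocol population would be used for sensitivity analysis of the analysis of the primary endpoint"; SAP 7.10 repeats this.

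SAP 7.15, which lists departures from the protocol, mentions dropping the full analysis set label and changing the KSS and VR-12 endpoints. It mentions no change to the per-protocol rule.

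**The concern.** The two specifications are conditions for being in the set, so a rule that removes a revised subject when either one is met runs the wrong way. Being eligible is enough to be removed.

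The endpoint is revision. Removing subjects because they were revised takes events out of the analysis and biases survivorship upwards. If all revised subjects are eligible, the literal rule returns 100% whatever the data show. With no events, a Greenwood interval has zero width and a log-log interval is undefined, so the planned Kaplan-Meier interval offers no usable check on the primary result.

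Correcting the negation does not fully settle the matter, because criterion (b) still requires attendance and the SAP omits the protocol's exemption from it.

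**Working it through.** **Step 1. Membership of a revised subject under each rule**

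| Revised subject | Protocol 9.3 | SAP 7.2 as written | SAP 7.2 with *is not met* |
|---|---|---|---|
| Eligible, no significant deviation, did not attend follow-up | in | out, (a) is met | out, (b) fails on attendance |
| Eligible, no significant deviation, attendance counted as met | in | out, (a) and (b) are met | in |
| Eligible, significant deviation | out | out, (a) is met | out |
| Ineligible and also fails (b) | out | kept by the revision sentence | out |

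As written, the SAP removes every eligible revised subject. With the negation corrected, the result depends on attendance. If attendance means the 2-year visit, a subject revised before it cannot attend, because participation ends at revision, and falls in the first row. If attendance covers only visits due before revision, the subject falls in the second row and the SAP essentially agrees with the protocol. Neither document says which is meant.

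**Step 2. The plan's own sample size**

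Inputs (protocol 9.1, SAP 6.1): reference survivorship 95.7%, margin 7%, bound 95.7 − 7 = 88.7%, n = 115. Exact binomial at one-sided 5%: success with at most 7 revisions, actual alpha 0.0446, power 0.877, which meets the stated minimum of 80%. Enrolment: 115/0.90 = 127.8, rounded up to 128. The stated figures reproduce.

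**Step 3. Effect on the estimate**

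Assumptions: 115 subjects, complete 2-year follow-up, all non-revised subjects kept, all revised subjects eligible. With complete follow-up the Kaplan-Meier estimate is p = x/n, where x is the number revision-free. The SAP names no interval method, so several are shown, with z = 1.96:

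- exact two-sided: 2.5% quantile of Beta(x, n − x + 1)
- exact one-sided (protocol 9.4): 5% quantile of the same distribution
- linear Greenwood: p − z√(p(1 − p)/n)
- log-log: p raised to the power exp(z√((1 − p)/(np))/|ln p|)

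With 8 revised, p = 107/115 = 0.9304:

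- linear: 0.9304 − 1.96 × 0.02372 = 0.8839
- log-log: exponent exp(1.96 × 0.3536) = 2.000, so 0.9304^2.000 = 0.8657
- zero events among the remaining 107, exact two-sided: 0.025^(1/107) = 0.9661

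| Revised of 115 | Survivorship | Exact two-sided | Log-log | Linear | Per-protocol, literal rule (exact two-sided) |
|---|---|---|---|---|---|
| 5 | 95.65% | 90.15% | 89.87% | 91.92% | 110/110, 100% (96.70%) |
| 8 | 93.04% | 86.75% | 86.57% | 88.39% | 107/107, 100% (96.61%) |
| 13 | 88.70% | 81.45% | – | – | 102/102, 100% (96.45%) |

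With 8 revised, the one-sided exact limit is 87.80%. All four limits are below 88.7%, while the literal per-protocol result clears the bound easily.

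**Step 4. Partial removal**

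If only some of the 8 are removed (for example, those revised before the 2-year visit when attendance means that visit):

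- 1 removed, 107/114: linear 89.45% passes; exact two-sided 87.76% and log-log 87.55% fail
- 2 removed, 107/113: exact two-sided 88.80% passes; log-log 88.56% fails
- 3 removed, 107/112: log-log 89.61% passes

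**Step 5. How likely these counts are**

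At the planning rate of 4.3% revised, the expected count is 115 × 0.043 = 4.9. The probability of 8 or more is 12.3%, and of 13 or more 0.14%. Thirteen is the expected count at the null boundary (115 × 0.113 = 13.0).

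**The case against.** The strongest reply is that nobody would apply the sentence literally. It says revised subjects retain membership, and a sentence written to keep them cannot sensibly expel all the eligible ones. The two specifications may be a loose paraphrase of the protocol's two exceptions, ineligibility and significant deviation. If revised subjects simply had to satisfy (a) and (b) like everyone else, the separate sentence would do nothing, which suggests that absence caused by revision was meant to be excused. SAP 7.15 declares no change, which also points to the protocol's meaning. On that view the 100% figures are a worst case.

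Much of this stands: the wording is probably a slip, and one corrected reading agrees with the protocol. But SAP 2 describes the document as the guideline for programming, and the question of attendance is not a typing error. It should not be settled after the revisions are known, particularly with largely retrospective data.

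Two further points limit the effect. The study's conclusion rests on the safety population in every scenario. The illustration also depends on n: with 8 of 128 revised and complete follow-up, the linear limit (89.56%) and one-sided exact limit (89.01%) pass, while exact two-sided (88.06%) and log-log (87.89%) fail. In addition, SAP 7.10 itself expects incomplete follow-up.

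The revision listing (SAP 5.4), accountability table (SAP 7.6) and flagged per-protocol exclusions (SAP 7.7) would let a reader notice missing revisions. They would not correct the estimate.

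**Conclusion.** The concern holds. The per-protocol rule for revised subjects in SAP 7.2 is wrong as written and contradicts protocol 9.3. With the negation corrected, one of the two possible meanings of attendance still contradicts it.

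The effect is confined to the per-protocol analysis; the primary non-inferiority test is untouched. Within that analysis the distortion can be complete: a study that misses the 88.7% bound with 8 of 115 revised would be accompanied by a sensitivity result of 100%. This rests on the assumptions in step 3 and on the literal reading. At the expected 5 revisions no conclusion changes. The point should be fixed, because this is the only sensitivity analysis the SAP names for the primary endpoint.

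**What to change.** Replace the sentence in SAP 7.2 with the protocol 9.3 rule, for example: *A subject with a device revision belongs to the per-protocol population whatever their follow-up attendance, unless they failed an inclusion or exclusion criterion or had a significant protocol deviation.* This also removes the need to define attendance for revised subjects. If a departure from protocol 9.3 is intended, declare and justify it in SAP 7.15.

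The cost is one sentence before database lock, with no extra data or analysis.

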7.3 Handling of Missing, Incomplete and Repeat Data

Not all subjects enrolled into this study would complete the study. Subjects who die or discontinue without a revision would have their data censored on their date of death/discontinuation. Subjects who do not have a revision by the end of the study would have their data censored at their last known study visit date.

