7.10 Analysis of Primary Endpoint

CONFIDENTIAL AND PROPRIETARY

This document contains information that is confidential and proprietary to Smith & Nephew PLC and Smith & Nephew, Inc. and is intended for use only by Smith & Nephew and its manufacturer. It shall not be reproduced or copied in whole or in part, nor shall the contents be disclosed by any means without prior written permission from Smith & Nephew, nor shall anyone make any use of it that is contrary to the expressed or implied wishes of Smith & Nephew.

Statistical Analysis Plan	smith&nephew
A Retrospective Study of the NAVIO Robotic-assisted Surgical System	Number: 16-NPFS-11
	Version: Final 1.0, Jan 29, 2018
	Page: 20 of 25

For the primary endpoint, cumulative proportion (or percentage) of subjects with implant survivorship at 2+ years (96 weeks), the following is the hypothesis would be performed:

H_0 (null): $S(t) = \pi \leq (\pi_0 - \delta)$ versus

H_a (alternate): $S(t) = \pi > (\pi_0 - \delta)$,

where π = expected percentage of subjects with implant survivorship at 2 years, π_0 = historical control implant survivorship (95.7%) and δ = margin of non-inferiority (7%).

Because not all subjects would be fully evaluated through study completion, the Kaplan-Meier product limit survival estimate would be used to estimate implant survivorship, $S(t)$ where $S(t)$ is the proportion of subjects at time t , without a device revision. Time to implant revision would be the endpoint of interest in the determination of implant survivorship.

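### Unrevised subjects who die or discontinue are censored at the exit date, not at the last confirmed implant status, which can bias 2-year survivorship upward

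*SAP*

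**What the plan says.** The primary analysis is time to revision: "the Kaplan-Meier product limit survival estimate would be used to estimate implant survivorship" (SAP 7.10). Non-inferiority is declared if the lower limit of the two-sided 95% interval at 2 years exceeds 88.7%.

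The SAP gives these censoring dates for unrevised subjects:

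- Death or discontinuation, SAP 7.3: "Subjects who die or discontinue without a revision would have their data censored on their date of death/discontinuation".
- Death or discontinuation, SAP 7.10: "A subject who prematurely discontinues from study as a result of death or for any other reason would be censored at the date" on which that event occurred.
- Loss to follow-up, SAP 7.10: "A subject who is lost to follow-up would be censored at the last known contact date". SAP 7.3 has no separate rule for this group.
- Unrevised at study end, SAP 7.3: "Subjects who do not have a revision by the end of the study would have their data censored at their last known study visit date".
- Completers, SAP 7.10: "Subjects who complete the study without a revision would be censored at their last known date in the study".

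Protocol 9.2 leaves the handling of missing data to the SAP, so these two sections are the only place where the matter is settled.

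**The concern.** Kaplan-Meier needs a subject to leave the risk set when observation of the event stops. A date of death or withdrawal marks the end of participation. It marks the end of observation only if implant status was known up to that day.

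This design leaves room for a gap between the two. All surgery precedes site approval (Protocol 5.3). Deceased and lost subjects may enter under a consent waiver, and living subjects may consent to the retrospective phase alone (Protocol 5.2). Retrospective implant status comes from the medical record as far as it is available (Protocol 6.2). A subject last seen at 6 months who dies at 26 months without a recorded revision would be counted as revision-free through 2 years.

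If revisions in such a gap go unseen, the risk set is too large and the estimate too high. On the only tested endpoint, that favours declaring non-inferiority. Separately, the two sections give different dates for the same subjects, so two programmers could derive different datasets.

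**Working it through.** **The plan's own figures.** Inputs are 95.7%, a 7-point margin, 115 evaluable subjects and 10% attrition (Protocol 9.1, SAP 6.1). The threshold is 95.7 − 7 = 88.7%. With an exact binomial test at one-sided 5% and n = 115, success needs at least 108 revision-free subjects; the exact error rate is 4.46% and power 87.7%. Enrolment is 115 / 0.9 = 127.8, so 128. Both figures reproduce, and this point does not affect them.

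**Assumptions not in the documents.** Constant revision hazard; a fraction d of subjects with status last known at 6 months; their exit date after 24 months; no revision in the gap detected (relaxed below).

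**Expected bias.** The hazard is λ = −ln(S) / 24 per month. After month 6 the affected subjects stay in the risk set but contribute no events, so the observed hazard is close to (1 − d)λ. The cumulative hazard at 24 months is then about λ[6 + 18(1 − d)].

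- True 88.7%: λ = 0.11991 / 24 = 0.004996. With d = 0.10, 0.004996 × 22.2 = 0.1109 and exp(−0.1109) = 89.5%, a rise of 0.8 points.
- True 95.7%: λ = 0.04395 / 24 = 0.001831. With d = 0.10, 0.001831 × 22.2 = 0.0407 and exp(−0.0407) = 96.0%, a rise of 0.3 points.
- True 88.7%, d = 0.30: 0.004996 × 18.6 = 0.0929 and exp(−0.0929) = 91.1%, a rise of 2.4 points.

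With d = 0.10 and status last known anywhere from month 3 to month 18, the rise is 0.3 to 1.0 points at a true 88.7% and 0.1 to 0.4 points at 95.7%.

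**False success at a true 88.7%.** Simulation with 128 subjects and at least 4,000 trials per cell. The lower limit comes from a log-log interval, which is a further assumption because the SAP names no transformation. Ranges cover repeated runs.

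| Affected | Gap revisions captured | Exit-date rule |
|---|---|---|
| 5% | none | 2.2–2.7% |
| 10% | half | 2.2–2.5% |
| 10% | none | 3.4–4.0% |
| 20% | none | 6.3–7.1% |
| 30% | none | about 11–12% |

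The nominal rate is 2.5%, one tail of a two-sided 95% interval. With nobody affected, the log-log interval gives 1.6 to 2.2%. In the rows with no capture and at least 10% affected, censoring at last documented status gives 1.3 to 1.8%. A plain Wald interval gives 6.7% at 10% affected with no capture, against 5.1 to 5.5% with last-status censoring.

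**The opposite case.** With 10% affected and every gap revision captured, the exit-date rule returns 88.7% at a true 88.7%, so it is unbiased. Cutting unrevised subjects back to 6 months while still counting later revisions gives about 87.9%, which is too low.

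**The case against.** The case for leaving the rule alone has five parts.

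- **Scope.** SAP 7.10 already censors lost subjects at last contact, and subjects unrevised at study end at a last visit or last known date. That leaves mainly deaths and other discontinuations. This stands, with one gap: SAP 7.3 has no loss-to-follow-up rule, and Protocol 7.1 lists loss among the reasons for termination, so a lost subject could be read into the discontinuation rule of 7.3.
- **Revisions may be captured.** Protocol 8 and 8.1 G require all revisions to be reported in every phase, and Protocol 8.2 has investigators ask about previous events at each prospective contact. This also stands: with full capture there is no bias. But a site cannot report a revision performed elsewhere after its last record, and neither document requires status to be confirmed at exit.
- **Few withdrawals fit.** Living subjects without a 2-year visit must consent first, and those who refuse contribute no further data (Protocol 5.2). Retrospective-only participants have not clearly discontinued. Fair; it lowers the likely number affected.
- **Size.** The planned 10% covers all attrition, including lost subjects. Even 4.0% is below the one-sided 5% of Protocol 9.4. True, but the SAP's own criterion implies 2.5%.
- **An existing check.** The per-protocol analysis requires follow-up attendance and would drop many unrevised non-attenders. It is a sensitivity analysis and does not correct the primary one.

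A reader might infer that the rule does inflate survivorship, or that false success reaches 11%. The documents support neither. They do not show that gaps exist or that revisions in them are missed, and nothing in them suggests that 20% or 30% of subjects would be affected.

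**Conclusion.** The point holds as a possible bias, not a demonstrated one. As written, the rule lets subjects who die or discontinue contribute revision-free time after their implant status was last known. Any resulting error favours non-inferiority. It needs both a gap and missed revisions within it.

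If the whole planned 10% is affected, under the 6-month gap and no-capture assumptions, the estimate rises by 0.8 to 0.9 points at the non-inferiority boundary and about 0.3 points at the planned 95.7%. False success is then about 3.4 to 4.0% with a log-log interval. It is about nominal with 5% affected or half of the gap revisions captured.

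The mismatch between SAP 7.3 and 7.10 rests on no assumption. For completers the two dates will often coincide, but the plan should name one. The change is inexpensive and worth making before database lock.

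**What to change.** Replace the censoring text in SAP 7.3 and 7.10 with one rule. Every unrevised subject is censored at the latest date on which implant status was confirmed, whether by clinic visit, medical record or telephone, and whatever the reason for leaving. Use the date of death or discontinuation only where status was confirmed to that date. State what counts as confirmation, so that revised and unrevised subjects are ascertained over the same period. Report the current exit-date rule as a sensitivity analysis.

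The work is SAP wording and one date derived from the implant status data that the schedule already collects.

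The statistical cost is real. Follow-up is shorter and power lower: at a true 95.7% with 10% affected and a log-log interval, about 87% falls to about 75%. Part of the higher figure comes from time that was never observed; with nobody affected, power is about 80 to 83%. Some downward bias remains if revisions are learned of after the last confirmed status while unrevised subjects are cut back to it. That is why a later confirmed date must be kept wherever one exists.
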